# 1.0 Objectives

1.1 Aim 1 (Phase 1): To conduct 5 focus groups for the development of two theory-based, video podcast-delivered, HIV prevention interventions for self-identified heterosexual African American males and females. Aim 2 (Phase 2): To evaluate the effectiveness of the two theory-based, video podcast-delivered, HIV prevention interventions for self-identified heterosexual African American males and females.

## 2.0 Background

2.1 There is a need to implement more evidence-based HIV prevention messaging in the African American community in order to mitigate HIV incidence and prevalence disparities. However, the resource expenditure associated with implementing evidence-based HIV prevention interventions may not coalesce with community resources and expertise available to successfully implement such interventions. Thus, the scientific premise for this mixed-methods study is grounded in 1) progressing the field of HIV prevention to create accessible and acceptable modes of science-driven interventions for behavior change; and 2) engaging the community as participants in the development of, as well as, recipients of HIV prevention science.

#### 2.2 NA

- African Americans in the U.S. continue to experience the highest rates of HIV incidence. African Americans are one of the most affected populations in the U.S., and HIV is among the top 10 causes of death among African Americans between 20 – 54 years old. Of the 37,968 newly HIV-infected persons in 2018, 42% were African American. The latest available data shows that HIV testing has decreased and HIV prevalence has increased in the state of Texas between 2015 and 2019. Likewise in Harris County, TX, the estimated HIV incidence rate has increased from 2018 to 2019, while HIV testing has showed a decrease during that time. HIV incidence has seen an increase among African Americans, ages 25 to 34, in particular. While men who have sex with men (MSM) comprise the majority of new HIV cases in 2018, heterosexual sexual contact comprised 34% of new cases among African Americans. Systems dynamics methodology has illustrated causal loops that suggest how heterosexual individuals may directly spread infection through heterosexual contact, but can also be directly infected by bi-sexual sexual contact and/or indirectly through homosexual sexual contact; indicating that, in a community system, the spread of HIV does not occur within a group-specific vacuum. Thus tackling HIV prevention among heterosexual African American individuals is also important.
  - 1. Heron M, Centers for Disease Control and Prevention. Deaths: Leading Causes for 2018, National Vital Statistics Reports, Vol 70(4).

https://www.cdc.gov/nchs/data/nvsr/nvsr70/nvsr70-04-508.pdf. Published May 17, 2021. Retrieved June 28, 2021.

- 2. Centers for Disease Control. HIV and African American People. https://www.cdc.gov/hiv/group/racialethnic/africanamericans/index.html. Published January 21, 2021. Retrieved June 11, 2021.
- 3. Centers for Disease Control. NCHHSTP AtlasPlus. http://www.cdc.gov/nchhstp/atlas/. Updated April 29, 2021. Accessed June 17, 2021.
- 4. Waring A. Practical System Thinking. Hampshire, UK: Cengage Learning EMEA; 1996.

### 3.0 Inclusion and Exclusion Criteria

- Phase 1 & 2: Individuals eligible to participate will: (1) self-identify as African American; (2) reside in a low SES predominantly African American super neighborhood; (3) speak and read English; (4) be 18 years old or older; and (5) not previously diagnosed with HIV. The screening questionnaire will assess these eligibility criteria (attached in the smartforms).
- 3.2 Phase 1 & 2: Potential participants will call dedicated university phoneline or email study team email account. Flyers will be distributed at African American-based community events; contact information will be displayed on the flyers.
- 3.3 The following groups will be excluded. The research may possibly involve economically and/or disadvantaged persons.
  - Adults unable to consent
  - Individuals who are not yet adults (infants, children, teenagers)
  - Pregnant women
  - Prisoners
  - Students for whom you have direct access to/influence on grades

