# 5.0 Number of Subjects

#### **LOCAL:**

- 5.1 Phase 1: Total number of subjects to be accrued locally = 35; Phase 2: Total number of subjects to be accrued locally = 128
- 5.2 NA The participant procedures involve no more than minimal risk.
- 5.3 Phase 1: We are seeking to conduct 5 focus groups with 7 people each. Phase 2: We are seeking to assess 128 African American adults (64 male; 64 female).

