Phase 2: Flyers will be distributed as indicated above. Inclusion criteria will be printed on flyers. Potential participants who presumably fit the study criteria and are interested will call the study phone or send correspondence via the study email and will be screened for eligibility. For phone screening: the potential participant will call the study hotline and be asked a series of short screening questions estimated to take approximately 3 minutes and answer any questions they may have, and get them formally enrolled, if applicable. If ineligible, the research team member will notify the potential participant that s/he is not eligible and thank him/her for interest as indicated in the screening script. For email screening: interested participants will email the study using the email provided on the recruitment flyer. A research team member will reply to them, asking all eligibility questions via email and ask that the potential participant send an email reply, responding to each screening question. If eligible, the research team member will enroll participant, assign a unique ID to participant, and email them the secure link which will include the consent form and pre-test. If ineligible (via email screening), the research team member will send a follow-up email notifying the potential participant that she is not eligible and thank the participant for their interest as indicated in the screening script.

6.4 Phase 1 & 2: Materials for recruitment include a study flyer indicating the abbreviated purpose of the study, solicitation for participation, eligibility criteria, incentives offered, and study contact information (phone and email). Phase 1 & 2 flyers are attached to the SmartForm.

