### 10.0 Procedures Involved

### 10.1 Study Design:

Phase 1: The study design is focus group methodology, a qualitative research design in which participants are guided through a freeform discussion of a particular issue. The results of will reflect perceptions about HIV that are validated directly from the participants themselves. Five focus groups will be conducted.

Phase 2: The study design is quantitative repeated measures methodology. Participant data will be de-identified and used aggregately in repeated measures analyses (N=128).

10.2 Phase 1: Participants will be introduced to the study and given written informed consent, with an opportunity to ask any study related questions. Participants will be notified that they will be digitally audio recorded throughout the duration of the focus group session. The moderator will introduce herself and instruct the participants to identify themselves with a pseudonym of their choice, and not to use their real names. The moderator will begin by asking the first question. Once discussion has begun, the moderator will guide the focus group discussion with a series of questions using the focus group script. [The focus group script of questions can be found in the SmartForms. The moderator will take notes throughout the focus group sessions that will provide context, if needed, throughout the discussion. The moderator will carefully watch the time, making sure that all questions are asked during discussion within the 1.5-hour time allotted for participation. Participants will be thanked for their participation, provided light refreshments, and will be given a Target, Amazon, or Wal-mart gift card of \$45 for participation.

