Phase 2: Participants will email or call a dedicated study email/phone line, where research assistants will screen them, answer any questions they may have, and get them formally enrolled, if applicable. Participants will be given a unique ID number. Participants will be emailed a secure unique link to the pre-test survey (which will include cover letter consent information – See Section 22.1). Participants will complete the pre-test measure. One month after pre-test survey completion, participants will be emailed a secure unique line to the post-test survey in which they will view the podcast video and complete the post-test measures. Participants will be emailed a secure unique link 3 months later to complete a brief behavioral outcome questionnaire. The research team will be knowledgeable about the podcasting software in order to assist participants in trouble-shooting, if necessary. Dark Light Studios will also provide consulting throughout the entire research process, if needed. Upon pre-test completion, participants will be emailed (or pick up in person) a \$20 Walmart, Target, or Amazon gift card; \$80 Walmart, Target, or Amazon gift card upon post-test completion; and \$25 Walmart, Target, or Amazon gift card upon 3 month follow-up completion; for an opportunity to receive \$125 for complete participation. For participants who do not have email addresses, research assistants will assist them in obtaining one, within the recruitment procedures, if desired; alternately, participants will be able to schedule a time to meet at one of the community centers in order to complete pre- and post-test surveys in person, and/or to pick up gift card, if needed.

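### Aim 2 concerns interventions for heterosexual men and women, but the plan as written neither requires nor records that identity; the quoted residence question also cannot establish criterion 2

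*Combined protocol and SAP*

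**What the plan says.** **Target population.** Section 1.0 words Aim 2 as follows: "To evaluate the effectiveness of the two theory-based, video podcast-delivered, HIV prevention interventions for self-identified heterosexual African American males and females". The background in section 2.2 ends its argument on the same group: "Thus tackling HIV prevention among heterosexual African American individuals is also important".

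**Eligibility.** Section 3.0, for both phases, states: "Individuals eligible to participate will: (1) self-identify as African American; (2) reside in a low SES predominantly African American super neighborhood". The other three criteria are English, age 18 or over, and no earlier HIV diagnosis. The section adds: "The screening questionnaire will assess these eligibility criteria (attached in the smartforms".

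**Sample and recruitment.** Section 5.3 gives the Phase 2 target: "We are seeking to assess 128 African American adults (64 male; 64 female". On the flyers, section 6.3 says: "Inclusion criteria will be printed on flyers". Section 6.4 adds that they also carry a short statement of the study's purpose.

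**Screening and survey content.** Section 10.3 describes the screening form by four items: age, race, language preference and Houston residence. The residence question it quotes asks whether the person now lives in the Houston MSA. The Phase 2 demographics it lists are age, sex, education and income.

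**Analysis.** Section 10.1 says: "Participant data will be de-identified and used aggregately in repeated measures analyses (N=128". Section 25.1 specifies repeated measures t-tests. No restriction or subgroup by sexual identity is described.

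**The concern.** An effectiveness aim that names a population needs either an entry rule that selects it or a recorded variable that identifies it. For Aim 2 the plan as written shows neither. Suppose participants who do not identify as heterosexual respond differently to material designed for heterosexual adults. The reported change would then mix two responses, with no means of separating them. Even if they respond the same way, a reader could not learn what share of the sample belongs to the group the aim is about.

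The residence criterion raises a smaller problem of the same kind: it defines who may enter, but the one question shown does not test it.

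**Working it through.** The plan gives no figure to reproduce on this point, so the check sets the sections side by side.

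**1. Where heterosexual identity appears**

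| Place | Items listed | Items on heterosexual identity |
|---|---|---|
| Aim 2 (1.0) | audience of the interventions | named |
| Inclusion criteria (3.0) | 5 | 0 |
| Exclusions (3.3) | 5 | 0 |
| Accrual target (5.3) | race, adulthood, sex | not mentioned |
| Screening form as described (10.3) | 4 | 0 |
| Phase 2 demographics (10.3) | 4 | 0 |

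**2. Could it be recovered from other listed data?** Section 10.3 lists five behavioral measures: intercourse frequency, unprotected intercourse, number of partners, HIV results, and condom use at last intercourse. As listed, none records identity or the partner's sex. The knowledge and attitude scales do not do so either.

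**3. Would the unseen screening form supply it?** Section 3.0 says the form assesses the listed criteria. A form that fully implements that list would not need an identity question. If the form does ask, section 3.0 is incomplete and still needs correcting.

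**4. What can be said about bias.** Let *p* be the share of participants outside the Aim 2 population, *H* the mean change in heterosexual participants and *O* the mean change in the others.

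- Overall mean change = (1 − *p*) × *H* + *p* × *O*
- Overall minus target-group change = *p* × (*O* − *H*)

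The documents give no value for *p*, *H* or *O*. The difference is zero if *O* = *H*, and may be positive or negative otherwise. Neither its size nor its sign can be derived.

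**5. Residence.** Criterion 2 has three components: a super neighborhood, its low SES, and its mainly African American population. A yes to the quoted question places a person in the metropolitan area and settles none of the three.

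**6. Can the gap still be closed?** Section 19.1 links each ID to the pre-test, post-test and follow-up surveys. Section 10.2 describes the last contact: "Participants will be emailed a secure unique link 3 months later to complete a brief behavioral outcome questionnaire". An item placed in any of the three surveys can therefore be joined to a participant's other data.

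**The case against.** **The phrase describes the interventions' audience, not the participants.** This stands for Aim 1. A reader might infer that focus-group members must be heterosexual, but Aim 1 says only whom the interventions are being developed for, so no Phase 1 mismatch is claimed. For Aim 2 the argument is weaker. Judging effectiveness for an audience requires knowing which participants belong to it.

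**Broad enrollment may be intended.** Section 2.0 frames the need in terms of the African American community, and section 2.2 says HIV spread is not confined to separate groups. This is possible. The aim should then say so, and the fix allows for it.

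**The attachments may fill the gaps.** The flyer carries the study's purpose and may name heterosexual adults, which could lead people to select themselves. That would be neither an entry rule nor a recorded variable. The screening form and survey are also unseen and may hold more than section 10.3 lists. The claim is therefore limited to the plan as written and, for residence, to the quoted question. A reader might also infer that earlier HIV diagnosis goes unscreened because section 10.3 does not list it. That would read too much into a summary list, when section 3.0 says the form covers the criteria.

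**No differential response is shown.** Correct. Outcomes such as condom use and HIV knowledge are not specific to heterosexual people, and the documents do not support a claim that the result is diluted or biased by any given amount.

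**Pooling of the sexes is not stated.** Also correct. The description of aggregate use does not say that men and women enter one test. The point does not depend on it, because analyses by sex would have the same gap.

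**Conclusion.** The point holds for Aim 2 and should be addressed. As written, people outside the population named in Aim 2 can be enrolled, and the listed data could not identify them. The effectiveness result therefore cannot be shown to apply to that population. This is a limit on applicability; the size and direction of any bias are unknown.

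Confidence is high that Aim 2 and section 3.0 do not match. It is lower that no unseen form records identity, since that rests on the lists in section 10.3 being complete.

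The residence point is secondary. The quoted question cannot establish criterion 2, but whether the form holds another residence item cannot be determined from the documents.

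**What to change.** 1. Add one optional sexual-identity item to the Phase 2 pre-test. For people already enrolled, place it in the post-test or 3-month survey by IRB amendment. First check that the existing consent covers it, because section 21.1 provides for no ongoing consent.
2. Report the share identifying as heterosexual, the number who did not answer, and the results in the heterosexual group beside the overall result.
3. Reconcile the text: either add heterosexual identity to section 3.0 and the screening form (and so to the flyers that print the criteria), or restate the Aim 2 population to match section 3.0.
4. Replace or supplement the MSA question with one that identifies the super neighborhood, or restate criterion 2 to match what is screened. If the attached forms already hold either item, list it in section 10.3.

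**Cost.** One or two short questions, one of them sensitive, and an amendment. The heterosexual analysis group would be somewhat smaller than the full sample. Recruitment may slow if identity becomes a criterion. An item added only at a later survey misses people who have already dropped out, so earlier is better.

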# 4.0 Vulnerable Populations

- 4.1 Additional safeguards to protect their rights and welfare of economically and/or educationally disadvantaged persons.
  - Phase 1 (focus groups): Individuals who are economically/educationally disadvantaged: Participants' incentives for research participation are proportionate with the risks. Participants will be paid \$45 for their participation. Discomforts and inconveniences involved in the research, and financial or other gains are not overly compelling. Consent documents are written in language that is easily understandable to participant. Research team will read consent document out loud for each participant and participant will

have the ability to ask questions. Eligibility criteria includes the ability to read and speak English.

Phase 2 (effectiveness phase): Individuals who are economically/educationally disadvantaged: Participants' incentives for research participation are proportionate with the risks. Upon pretest completion, participants will be emailed (or pick up in person) a \$20 Walmart, Target, or Amazon gift card; \$80 Walmart, Target, or Amazon gift card upon post-test completion; and \$25 Walmart, Target. or Amazon gift card upon 3 month follow-up completion; for an opportunity to receive \$125 for complete participation. (For participants who do not have email addresses, research assistants will assist them in obtaining one; alternately, participants will be able to schedule a time to meet at one of the community centers in order to complete pre- and post-test surveys in person, (and/or to pick up gift card) if needed.) Discomforts and inconveniences involved in the research, and financial or other gains are not overly compelling. Consent documents are written in language that is easily understandable to participant. Participants will email or call a dedicated study email/phone line, where research assistants will screen them, answer any questions they may have, and get them formally consented and enrolled, if applicable. Eligibility criteria includes the ability to read and speak English.

# 5.0 Number of Subjects

#### **LOCAL:**

- 5.1 Phase 1: Total number of subjects to be accrued locally = 35; Phase 2: Total number of subjects to be accrued locally = 128
- 5.2 NA The participant procedures involve no more than minimal risk.
- 5.3 Phase 1: We are seeking to conduct 5 focus groups with 7 people each. Phase 2: We are seeking to assess 128 African American adults (64 male; 64 female).

### 6.0 Recruitment Methods

#### LOCAL:

6.1 When and Where: Phase 1 - Rolling recruitment and focus group facilitation will occur over 3 months (Year 1). Participants will be recruited through postings on community bulletin boards in African American communities and churches, at public community events within African American communities, and at events held by UH HEALTH Research Institute (HRI). Flyers and email list serves will be used to recruit participants. Community based service organizations that serve many

predominantly African American communities will assist in the active recruitment of participants as well (see letters of support). [name], an established investigator, faculty mentor, and collaborator for the associated grant proposal submission, currently serves as director at the HRI and will assist in recruitment efforts via the center's community engagement core.

Phase 2: Participants will be recruited on a rolling basis with the assistance of community partners, through postings on community bulletin boards, and flyers at public community events within African American communities; as well as at events held by HRI (virtually or in-person), and the center's RCMI websites; as well as with the assistance of community partners (see letters of support).

Appropriate permissions for recruitment at the above-mentioned locations are ensured: Community partner support for recruitment at their local events is evidenced through the community partner letters of support (attached in the smartforms), the funded project will be conducted through the HRI which lend their recruitment support for all projects funded within their center (i.e., the HRI community engagement core), and community bulletin postings are free for public use.

- 6.2 Participants will be sourced from community events (market gatherings, various local festivals, events held by community partners) and through HRI events throughout the African American community.
- 6.3 Methods and materials for recruitment:

Phase 1: Flyers will be distributed as indicated above. Inclusion criteria will be printed on flyers. Potential participants who presumably fit the study criteria and are interested will call the study phone or send correspondence via the study email and will be screened for eligibility. For phone screening: the potential participant will call the study hotline and be asked a series of short screening questions estimated to take approximately 3 minutes. If eligible, the research team member will inquire on the preferred participation day/time (during one of the evening or weekend focus group sessions). If ineligible, the research team member will notify the potential participant that s/he is not eligible and thank him/her for interest as indicated in the screening script. For email screening: interested participants will email the study using the email provided on the recruitment flyer. A research team member will reply to them, asking all eligibility questions via email and ask that the potential participant send an email reply, responding to each screening question. If eligible, the research team member will reply with a list of available study day/times and ask the participant to reply with the most convenient time she wishes to participate. After confirming her preferred time, s/he will be sent a confirmation email to participate in the scheduled focus group. This constitutes a total of three email exchanges. If ineligible (via email screening), the research team member will send a follow-up email notifying the potential participant that she is not eligible

and thank the participant for their interest as indicated in the screening script.

Phase 2: Flyers will be distributed as indicated above. Inclusion criteria will be printed on flyers. Potential participants who presumably fit the study criteria and are interested will call the study phone or send correspondence via the study email and will be screened for eligibility. For phone screening: the potential participant will call the study hotline and be asked a series of short screening questions estimated to take approximately 3 minutes and answer any questions they may have, and get them formally enrolled, if applicable. If ineligible, the research team member will notify the potential participant that s/he is not eligible and thank him/her for interest as indicated in the screening script. For email screening: interested participants will email the study using the email provided on the recruitment flyer. A research team member will reply to them, asking all eligibility questions via email and ask that the potential participant send an email reply, responding to each screening question. If eligible, the research team member will enroll participant, assign a unique ID to participant, and email them the secure link which will include the consent form and pre-test. If ineligible (via email screening), the research team member will send a follow-up email notifying the potential participant that she is not eligible and thank the participant for their interest as indicated in the screening script.

6.4 Phase 1 & 2: Materials for recruitment include a study flyer indicating the abbreviated purpose of the study, solicitation for participation, eligibility criteria, incentives offered, and study contact information (phone and email). Phase 1 & 2 flyers are attached to the SmartForm.

